vital signs the subject will be shown the treadmill and instructed in proper and safe use. The settings will be increased until the desired minute ventilation is reached. A urine pregnancy test will be repeated on those for whom it is applicable. Vitals signs, including temperature HR, RR, BP, and SpO₂, will be collected before and after treadmill exercise. Spirometry will be performed before exercise begins. Subjects will exercise for 15 minutes, during which time the treadmill will be adjusted to the subjects comfort and to reach the desired minute ventilation. They will then rest for 15 minutes, followed by another 15 minute exercise period to confirm the degree of exercise and the treadmill settings. Subjects will be monitored with cardiac telemetry during the treadmill period, and vital signs will be measured after exercise is complete.

A baseline MCC scan, including a transmission scan, will be completed following the treadmill training. (Full description in section f.)

Nasal epithelial lining fluid (ELF) samples will be obtained from both nares. Nasal epithelial cells (NEC) will be obtained from the right nare.

Subjects will be required to return to the research lab 24 hours after the baseline MCC for a 30 minute follow up scan. (V0b).

III. DOSING:

(Visit 1 and 4)

At Visit 1, subjects will be randomized to receive either active gamma tocopherol or safflower oil placebo. Visit 1 must occur within one month of the baseline visit. Visit 1 may be combined with Visit 0a.

1. Vitals signs will be measured.
2. Urine pregnancy test will be performed on all women of childbearing potential.
3. Spirometry will be performed.
4. Exhaled NO will be measured.
5. Sputum induction will be performed.
6. Subjects will be given study drug prepared by the Investigational Drug Service and instructed to take the first dose of study drug the evening of the visit, 2 days prior to the planned exposure. The second dose will be taken 12 hours later, in the morning on the day prior to the exposure. Dose three will be taken 24 hours after the first dose. The final dose will be taken on the morning of the exposure, 12 hours after dose 3.

IV. OZONE CHALLENGE (after 4 doses of study drug)

(Visit 2 and 5):

Pre-Exposure

1. Urine pregnancy testing if applicable
2. Vital signs
3. Ozone Symptom questionnaire
4. Exhaled NO measurement
5. Spirometry
6. Subject will undergo brief physical examination prior to exposure

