7. Blood samples obtained for phagocytic function, γ T, γ T metabolite, α T, cytokines, proteins, immune and inflammatory markers, eicosanoids, glutathione levels, PT, aPTT, CBC with differential, CRP, plasma lipids, and other antioxidants, as well as flow cytometry studies; RT-PCR will also be performed for gene expression studies.
8. ELF samples will be collected.
9. Standard telemetry monitoring will commence

Ozone exposure (0.25 ppm)

1. The subject enters the chamber, and proceeds to the treadmill. This is time point 0 for data collection. Exercise starts at the settings determined on the training day.
2. Minute ventilation is measured at 8 minutes into the exercise period, and again at 12 minutes, for 2 minutes each time. For subsequent exercise sessions, minute ventilation will only be measured at the 12 minute mark.
3. The subject will exercise for 15 minutes, followed by 15 minutes of rest. This cycle is repeated for a total of 3 hours, for **6 exercise and 6 rest periods**.
4. Blood pressure will be measured at least once an hour while they are in the chamber.
5. Symptom scoring will be done immediately prior to exiting the chamber.

Post-Exposure

1. Spirometry and vital signs will be measured immediately post exposure.
2. Elf samples will be collected.
3. Spirometry will be collected again at approximately 30-45 minutes post completion of the exposure.
4. One hour after O₃ exposure is completed, the subject begins the MCC scan procedures. Spirometry will only be collected during MCC scanning if the subject has distress.
5. At completion of MCC, vital signs and spirometry will be obtained. This should be approximately 6 hours after the beginning of the exposure time point.
6. Post-exposure blood samples will be collected.
7. Sputum induction, with albuterol pre-treatment.
8. Elf samples will be collected.
9. NEC will be collected from the left nare.
10. Subjects will return to the gamma camera for a final 10-minute scan.
11. Discharge home with contact information for a study physician.

V. FOLLOW-UP:

(Visit 3 and 6)

Subjects will arrive in the research lab approximately 24 hours after the start of the exposure.

Subjects will undergo:

1. 30 minute follow up MCC scan.
2. Vital sign collection and symptom scoring
3. Blood sample collection
4. Exhaled NO

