Markers of inflammatory cell activity: To assess neutrophil activity in the airway, we will assay sputum for myeloperoxidase (MPO) and 5-chlorouracil (a product of the action of HOCL derived from neutrophil MPO and nucleobases of injured cells, and a marker of PMN oxidative burst). To assess for eosinophil activity, we will assay sputum for eosinophil cationic protein (ECP) and 5-Bromouracil (a product of the action of HOBr derived from eosinophil peroxidase and nucleobases of injured cells, and a marker of eosinophil oxidative burst). Reactive nitrogen oxide species (RNOS) such as peroxynitrite are generated by inflammatory cells following stimulation with inflammatory irritants and sputum and plasma samples will be assayed for 5-Nitro-γ-tocopherol, a product of the action of RNOS on γT.

Nasal epithelial lining fluid: We will examine epithelial lining fluid for levels of inflammatory cytokines, including (but not limited to) GM-CSF, IL-1β, IL-4, IL-6, IL-8, IL-13, IL-17, RANTES, eotaxin and TNFα. We will also examine levels of metalloproteinases and eosinophil cationic protein.

Nasal epithelial cells: We will analyze mRNA isolated from nasal epithelial cells using a customized Nanostring immune panel to assess expression levels of genes involved in innate immune and oxidant stress responses before and after ozone challenge. Genes examined will include those implicated in various aspects of epithelial-driven inflammatory responses, such as those associated with epithelial barrier integrity (apical junction complex proteins), epithelial-derived danger signals, pro-inflammatory chemokines/cytokines, PRRs (pattern recognition receptors), downstream targets of PRR signaling, and genes associated with the antioxidant response element.

Other Antioxidants in plasma and sputum samples: These measures will be provided by the Biochemistry Core of the UNC Clinical Nutrition Research Unit and may include reduced and oxidized glutathione, catalase, glutathione peroxidase, glutathione reductase, and superoxide dismutase.

4. Hypertonic Saline Induced Sputum procedure:

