Airway inflammation will be evaluated using the NIOX MINO device, following ATS, 2005 recommendations and the manufacturer's instructions. Since spirometry can potentially impact the nitric oxide (NO) measurement, the FeNO test needs be completed prior to spirometry. In addition, subjects should not eat or drink 1 hour prior to having the FeNO, as this may affect the results.

7. Nasal Epithelial Lining Fluid (ELF): Nasal ELF will be sampled with a small strip of Leukosorb paper inserted gently by means of direct vision into the nasal cavity laterally against the anterior portion of the inferior turbinate. Sterile saline solution is transferred into a mist bottle (the same one used for NL) and subjects are asked to moisten their nasal passages with a single spay into each nostril. A nasal clip will be applied, and the Leukosorb paper will be left for absorption for 2 minutes. Subjects will be required to breathe though the mouth during this time. Thereafter, the Leukosorb strip will be removed and immediately stored at 80°C.

8. Nasal Epithelial Cells (NEC): a non-invasive biopsy procedure will be performed to retrieve a small cluster of cells from each of the nasal cavities. For the nasal biopsy procedure, the subject will be seated comfortably in a straight-backed chair or reclining on an examination table with the head tilted as far back as possible while remaining comfortable. Subjects will be given no medication, sedation, or anesthesia for this procedure. A short, sterile plastic sampling device called a curette will be inserted into one of the nasal cavities and the surface of the nasal cavity will be stroked several times for approximately 5 seconds in order to obtain a small cluster of cells. This maneuver will be repeated on the contralateral nasal cavity using a fresh curette. The nasal biopsy may only be obtained from 1 nostril during a visit.

9. Regional Deposition and Mucociliary Clearance (MCC) procedures:

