Risks to subjects: At the doses proposed in this study, the most significant predictable risk to subjects as a result of ozone inhalation is development of airway inflammation which would cause shortness of breath, cough or wheeze. Ozone is known to cause a temporary inhibition in the ability to take a deep breath – this is transient and typically declines within 2 hours of completion of exposure, though it may take up to 72 hours for complete resolution. At high doses, tocopherols can increase coagulability, though we have not observed this in other studies using gamma tocopherol. Nausea and upset stomach have been reported, subjects are asked to take the supplement with food. Sputum induction may induce bronchospasm. Venipuncture carries a risk for hematoma. There is a slight risk of sneezing with ELF collection, subjects who may not be able to tolerate the paper will not be asked to continue with this measurement. Nasal epithelial biopsy is a transiently irritating procedure, and it presents a rare risk of nose bleed.

Measures to minimize risk: Only volunteers who have normal lung function will be recruited for this project. Further, subjects will be deferred for challenge until 4 weeks after complete resolution of each of the following acute illnesses: viral respiratory tract infection, pneumonia or bronchitis requiring antibiotic therapy (must be off antibiotics and well for 2 weeks after the last dose of antibiotics, 4 weeks in the case of azithromycin due to its prolonged half-life), or acute illness resulting in fever. Also, unspecified illnesses, which in the judgment of the investigator increase the risks associated with ozone inhalation challenge, will be a basis for exclusion. As outlined above in section "d", all subjects will need to fulfill objective lung function and symptom criteria prior to initiating a specific challenge study. Subjects will be questioned about their previous radiation exposure history. Subjects whose exposure history

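### Nasal cells come from the right nostril before ozone and the left after it in every subject, so the exploratory ozone change in nasal gene expression is aliased with side

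*Protocol*

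**What the plan says.** **Nasal cells.** Protocol Outline, II. Training (V0a): "Nasal epithelial cells (NEC) will be obtained from the right nare". Protocol Outline, IV. Ozone Challenge, Post-Exposure item 9, which applies to V2 and V5: "NEC will be collected from the left nare". The visit table lists NEC at V0a, V2 and V5 only, so there is no pre-exposure NEC sample on an ozone day. Section VII (Crossover) says to repeat step II. Followed literally, that would add a second training sample, also right-sided.

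**Purpose.** Section d gives a pre- and post-ozone nasal comparison as the reason for the baseline nasal samples. Section f.3 describes the NEC endpoint as expression of genes in immune and oxidant stress "responses before and after ozone challenge".

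**Nasal fluid.** At V0a, "Nasal epithelial lining fluid (ELF) samples will be obtained from both nares". On ozone days fluid is taken before exposure, immediately after it, and at about 6 hours, this last just before the NEC sample. It is taken again at V3 and V6. No nostril is named after V0a.

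**Procedure.** Section f.8 states "This maneuver will be repeated on the contralateral nasal cavity using a fresh curette" and then "The nasal biopsy may only be obtained from 1 nostril during a visit". Section g notes that "Nasal epithelial biopsy is a transiently irritating procedure".

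**Analysis.** The SAP has no term for nostril or previous biopsy and describes no specific model for the NEC data. The design has no filtered-air session.

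**The concern.** A before/after comparison within a person is informative only if what changes between the samples is the exposure, or if the other changes can be estimated and removed. Here nostril changes with exposure in every subject and in the same direction. Any average difference between left and right, whether biological or from the way the operator samples each side, would be reported as an ozone effect or would mask one. More subjects would not help.

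What is at stake is the interpretation of the ozone response in nasal gene expression. That is a stated exploratory result and the natural reference for judging whether gamma tocopherol reduces the response. The 24-hour nasal fluid raises a related but conditional question: if the sampled nostril was scraped the day before, a rise in inflammatory cytokines could come from the scrape.

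**Working it through.** The plan gives no figure on this point, so the check is one of estimability.

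**1. NEC layout for each subject**

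| Visit | Ozone | Nostril | Study drug |
|---|---|---|---|
| V0a | before | right | none yet |
| V2 | after | left | first treatment |
| V5 | after | left | second treatment |

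The ozone and nostril columns are identical. Write O for the ozone effect, δ for left minus right, and D for all other differences between V0a and the exposure visits. Ignoring treatment, the expected post minus pre change is O + D + δ.

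**2. Rank.** A linear model with subject, ozone, side, treatment × ozone and period, laid out for eight illustrative subjects, has 8 + 4 = 12 columns and rank 11. Neither ozone nor side is estimable. The rank stays at 11 if the training visit is repeated in period 2.

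**3. Treatment contrast.** The same V0a sample is the baseline for both periods, so (V2 − V0a) − (V5 − V0a) = V2 − V5. Both are left-sided, so δ cancels. The rank check agrees: the treatment effect is estimable. Only an interaction of treatment with side would remain.

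**4. Effect of counterbalancing.** Let n1 subjects be right-first and n2 left-first. The expected change is O + D + δ in the first group and O + D − δ in the second. Half the difference of the group means estimates δ; their simple average estimates O + D. With side alternated the matrix has rank 12 of 12.

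Without a side term, the pooled mean keeps a residual of δ(n1 − n2)/(n1 + n2). With a side term, the precision for O + D equals that of 4·n1·n2/(n1 + n2) balanced subjects. The documents do not say how many subjects had been sampled, so the early number is an assumption. Early subjects stay right-first, and the rest of 32 are split equally:

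| Assumed early | n1 / n2 | Residual, no side term | Equivalent balanced n, side fitted |
|---|---|---|---|
| 0 | 16 / 16 | 0 | 4·16·16/32 = 32 |
| 8 | 20 / 12 | 8/32 = 0.25 δ | 4·20·12/32 = 30 |
| 16 | 24 / 8 | 16/32 = 0.50 δ | 4·24·8/32 = 24 |
| 32 (as written) | 32 / 0 | 1.00 δ | not estimable |

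**5. What D contains.** V0a precedes dosing, whereas four doses precede each exposure. Exercise is 2 × 15 = 30 minutes at V0a and 6 × 15 = 90 minutes in the chamber. Sputum induction with albuterol precedes NEC at V2 and V5, but is not scheduled at V0a unless V1 is combined with it. The dates also differ. Counterbalancing side leaves all of D in place.

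**6. Nasal fluid.** The post-scan assessments fall about 6 hours after exposure starts. Blood, sputum induction and fluid follow, so NEC falls at about 6 to 7 hours. V3 and V6 are at about 24 hours, a gap of about 24 − 7 = 17 to 24 − 6 = 18 hours. If the left nostril is used, a model for the exposure-day and 24-hour samples (four illustrative subjects; three time terms, recent biopsy, treatment, three treatment × time terms and period: 4 + 9 = 13 columns) has rank 12. The 24-hour ozone change and the biopsy effect cannot be separated. The immediate and 6-hour changes, and treatment × time at all times including 24 hours, are estimable.

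**The case against.** The strongest reply is that the trial asks whether gamma tocopherol alters the ozone response, and that comparison is protected by taking the same side in both periods. This stands, for NEC and for 24-hour fluid alike. A reader might infer that the nasal treatment comparison is compromised; additive side or biopsy effects cancel from it.

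Second, nothing in the documents shows a systematic left/right difference. Differences that vary at random between people add noise, not bias. This also stands: the rank deficit shows that the side effect cannot be checked, not that it is large.

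Third, the pre/post NEC change is confounded with other things anyway. That is correct, and it limits what the fix achieves. It is no reason to keep a confounder that is easily removed.

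Fourth, opposite nostrils may be deliberate, to avoid scraping a recently sampled site. Counterbalancing keeps the V0a and post-ozone samples on opposite sides.

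Fifth, the 24-hour fluid may already include a nostril not biopsied the day before. It may, which is why that part is conditional.

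Finally, the two f.8 sentences need not conflict. They can mean that each cavity is sampled, but at different visits, which fits the visit instructions. If they meant both sides at every visit, the side alias would vanish. A reader might call them a flat contradiction; the text supports only a request to reconcile the wording.

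**Conclusion.** As written, the exploratory pre/post-ozone change in nasal gene expression is completely aliased with nostril side, in up to 32 subjects. This rests on the visit instructions being followed as stated, one nostril per visit. The size of the bias is δ, which the documents do not give and the design cannot estimate. The primary sputum endpoint and the gamma tocopherol versus placebo contrast are unaffected.

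Two stronger conclusions are not supported. One is that removing the side alias would isolate the ozone effect: date, dosing, exercise and sputum induction would still differ between V0a and V2 or V5. The other is that the 24-hour nasal fluid is necessarily contaminated by the biopsy: that depends on an unstated nostril, and the immediate and 6-hour fluid samples precede that visit's biopsy. The point is worth acting on because the remedy is cheap, but it concerns exploratory data only.

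**What to change.** 1. **NEC side.** For subjects not yet sampled, alternate or randomise the nostril used at V0a, balanced within treatment sequence, and use the opposite nostril at V2 and V5. Record the side and include it in any pre/post NEC model.
2. **Model side; do not assume that it cancels.** The February 2017 summary of changes says several subjects had already gone through various visits. If they stay right-first, the split will be unequal and order will partly track enrolment date. A sensitivity estimate of side from the concurrently alternated subjects alone would address the latter.
3. **If sampling is complete,** report the pre/post NEC change as descriptive, state that it compares right with left, and rest inference on the treatment contrast.
4. **24-hour nasal fluid.** State the nostril at each visit. At V3 and V6, take or separately analyse fluid from the nostril not biopsied the day before, and compare it with that nostril's own pre-exposure sample. That nostril was biopsied at V0a, which can fall only about two days before V2 if V1 is combined with V0a, so record the interval.
5. **Wording.** Reconcile the two f.8 sentences, and reconcile the instruction in section VII to repeat step II with the visit table, which shows V0a once.

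Cost: a line in the visit instructions, a recorded side and one model term. No extra NEC sample, visit or subject is needed. Unequal groups lose some precision, as shown in the working.

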5. ELF
6. Spirometry

Subjects will be discharged with Ozone Symptom questionnaires to be filled out on each of the 4 days following the Follow-Up Visit, and with contact information for a study physician.

A follow up phone call will be made to the subject approximately 7 days after discharge.

VI. WASHOUT PERIOD

Subject will not take any study treatment for a minimum of 3 weeks and a maximum of 3 months.

VII. CROSSOVER

Subject will repeat steps **II** and **III** with the SO (placebo) if they received yT before crossover, or the subject will receive yT if they received SO before crossover.

VIII. END OF STUDY VISIT:

(Visit 7)

Within 5-10 days of the final challenge dose, each subject will be asked to return for a study discontinuation visit. At that time, the following assessments will be performed: vital sign measurement including O₂ saturation; lung function (FVC and FEV1); CBC, PT and aPTT (if abnormal values at Visit 6) and Ozone Symptom questionnaire. If any of these suggest lingering effects of ozone exposure, medical evaluation as directed by the study physician will be undertaken.

The table below summarizes the procedures at each visit:

Assessment/ Procedure	V0	V0a	V0b	V1	V2	V3	V4	V5	V6	V7
Informed consent	X									
Medical History	X									
Review history/AE's		X		X	X	X	X	X	X	X
Record Concomitant meds	X	X		X	X	X	X	X	X	X
Urine pregnancy test	X	X		X	X		X	X		
Vital signs	X	X		X	X	X	X	X	X	X
12 lead ECG	X									
Spirometry	X	X		X	X	X	X	X	X	X
Physical exam	X				X			X		X***
Blood draw	X				X*	X		X*	X	X***
Ozone Symptom Questionnaire					X**	X		X**	X	X
Sputum Induction	X			X	X		X	X		
Exhaled NO	X	X		X	X	X	X	X	X	
ELF		X			X**	X		X**	X	
NEC		X			X			X		
Telemetry		X			X			X		
Treadmill training		X								
Study drug dispensed				X			X			
Medication Diary disp.				X			X			

Lung transmission scan		X			X			X		
MCC		X			X			X		
Follow-up scan			X			X			X	
Ozone challenge					X			X		

*These assessments are performed twice at this visit – before ozone exposure and after ozone exposure

**These are performed three times at this visit – pre-exposure, immediately post- and 6 hours post- exposure

*** These are done as needed, as determined by the study doctor.

e. Dosage:

1. Gamma Tocopherol:

This section outlines CMC information on the ozone used as a challenge agent in a dose-ranging clinical study to assess the effect of pre-treatment with a single dose of inhaled fluticasone propionate on lung inflammation following challenge with inhaled ozone and intermittent exercise in healthy volunteers, relative to placebo. This amendment includes details of the description, composition, and manufacturer, method of manufacture, specifications and analytical methods.

2. Ozone (Challenge Agent)

Description

As described in the IND, Ozone is a highly reactive gas that is commonly found as a major component of photochemical smog and acute exposure to ozone is known to cause airway inflammation. For the purpose of this challenge study, exposures to ozone via inhalation are conducted in a 4 x 6 x 3.2 m stainless-steel chamber with continuous reconditioning of the chamber air through high-efficiency particle filters. Ozone is generated by exposure of oxygen to a silent electric arc in an ozone generator. The concentration of the ozone is continuously monitored to ensure that the appropriate concentration is maintained.

Composition

The chamber atmosphere will be maintained by continuous conditioning of the chamber air to ensure a composition of ozone of 0.25 ppm (± 0.0125 ppm) over 3 hours at $22^{\circ}\text{C} \pm 1.1^{\circ}\text{C}$ and 40% RH $\pm 5\%$ RH.

Manufacturer(s)

The ozone is made in-situ for use in the environmental chamber that is located as follows:

EPA Human Studies Facility
[name]
Chapel Hill
NC 27599-7315

Method of Manufacture

Ozone is generated by a Fischer, model 502 ozone generator (Meckenheim/Bonn, Germany). The generator uses oxygen which passes through a silent electric discharge to generate ozone. The ozone concentration and output is controlled by varying the flow of oxygen through the generator and by varying the power of the silent electric arc. The ozone is mixed with the air to obtain a desired concentration. The resulting ozone enriched air is then introduced into the environmental chamber to allow exposure via inhalation.

The concentration of ozone is continuously¹ monitored using UV photometric analyzers. The analyzers are connected to the Analyzer Support System comprising of:

- (1) Analyzer Function Support System. This provides vacuum and gas shut-off valves, and potentiometers for the mass-flow controllers;
- (2) Analyzer Calibration System. This consists of equipment to provide accurate calibration of the gas analyzer;
- (3) Analyzer Alarm System. Comprises computer software which controls alarms (both sound and visual (light) warnings) and gas shut-off valves.

Description of the Manufacturing Process

The ozone delivery system comprises the following components:

Gas supply bottles and manifolds in the bottle house with oxygen cylinders;
Gas delivery panels;
Gas injection system;
Ozone generator;
Deionized water system;
Computers and computer interfaces.

Stainless steel gas plumbing is used to deliver oxygen to the pollutant delivery system on demand. Mass-flow controller precisely control the amount of oxygen that is supplied to the zone generator and subsequently mixed with facility makeup air. To ensure that the flow of oxygen is not interrupted, each gas manifold (equipped with a pressure regulator) will automatically change from one bank of cylinders to another. The line pressure, of approximately 50 psig, is monitored by a computer. Deionized water is used to humidify the air.

f. Observations and Measurements

- 1. Primary Endpoints:** The primary efficacy endpoint (airway neutrophils/mg in the sputum) will be assessed by post-O₃/pre-O₃ ratio of log sputum PMNS/mg, comparing the ratios during the placebo treatment to the active treatment arms.
- 2. Safety measurements:** Symptom scores, lung function tests, PT and aPTT and platelet counts will be assessed as safety measures. Tocopherols in high doses may rarely have an effect on coagulation.
- 3. Exploratory Endpoints:**

Cytokines and other proteins at baseline and in response to ozone: We will examine sputum and plasma samples for levels of inflammatory cytokines, including (but not limited to) GM-CSF, IL-1 β , IL-4, IL-5, IL-6, IL-8, IL-10, IL-13, RANTES, eotaxin and TNF α . Also to be examined are metalloproteinases, mast cell tryptase, eosinophil cationic protein and eosinophil derived neurotoxin. CRP will also be measured at baseline and 24hr post-exposure.

Airway and blood phagocyte function: We have observed that inhalation of inflammatory stimuli (including ozone and ozone) is associated with changes in cell surface markers of monocytes, macrophages, and neutrophils, especially CD11b (CR3 receptor, associated with response to complement and egress of cells from the circulation to tissue), CD16 (Fc γ I receptor for IgG), CD64 (Fc γ III receptor for IgG), CD45 (pan leukocyte marker), CD80 and CD86, MHC class II molecules, and CD14 (an endotoxin receptor). We have also observed that the ability of monocytes and macrophages to phagocytize opsonized zymosan is blunted following challenge with inhaled inflammatory stimuli ⁽¹⁾. Similar observations have been made in asthmatics with increased eosinophilia ⁽²⁾. We will examine the effect of γ T supplementation on these important parameters of host defense.

Microarray analysis: We will analyze mRNA isolated from sputum macrophages and granulocytes using DNA microarray technology to assess genes involved in innate immune and oxidant stress responses before and after ozone challenge. We will also analyze protein mediator profiles of these cells using the sputum supernatants. These techniques will allow us to examine if γ T supplementation modifies innate immune and oxidant stress responses.

Immune Markers: We will also examine cell surface markers of lymphocyte subsets (CD3, CD4, CD8, CD45), monocytes (CD14), NK cells (CD16/56), B cells (CD19/20) and markers relevant to allergic responses (CD23, FcERI)

Eicosanoids: We will examine sputum and plasma samples for levels of cyclooxygenase pathway products (PGE₂, PGF_{2α}) and lipoxygenase pathway products (LTB₄, LTC₄, LTD₄, LTE₄) as γT has observed actions on eicosanoid production.

Plasma lipids: Panel will include cholesterol, LDL, VLDL and HDL and triglycerides.

Markers of inflammatory cell activity: To assess neutrophil activity in the airway, we will assay sputum for myeloperoxidase (MPO) and 5-chlorouracil (a product of the action of HOCL derived from neutrophil MPO and nucleobases of injured cells, and a marker of PMN oxidative burst). To assess for eosinophil activity, we will assay sputum for eosinophil cationic protein (ECP) and 5-Bromouracil (a product of the action of HOBr derived from eosinophil peroxidase and nucleobases of injured cells, and a marker of eosinophil oxidative burst). Reactive nitrogen oxide species (RNOS) such as peroxynitrite are generated by inflammatory cells following stimulation with inflammatory irritants and sputum and plasma samples will be assayed for 5-Nitro-γ-tocopherol, a product of the action of RNOS on γT.

Nasal epithelial lining fluid: We will examine epithelial lining fluid for levels of inflammatory cytokines, including (but not limited to) GM-CSF, IL-1β, IL-4, IL-6, IL-8, IL-13, IL-17, RANTES, eotaxin and TNFα. We will also examine levels of metalloproteinases and eosinophil cationic protein.

Nasal epithelial cells: We will analyze mRNA isolated from nasal epithelial cells using a customized Nanostring immune panel to assess expression levels of genes involved in innate immune and oxidant stress responses before and after ozone challenge. Genes examined will include those implicated in various aspects of epithelial-driven inflammatory responses, such as those associated with epithelial barrier integrity (apical junction complex proteins), epithelial-derived danger signals, pro-inflammatory chemokines/cytokines, PRRs (pattern recognition receptors), downstream targets of PRR signaling, and genes associated with the antioxidant response element.

Other Antioxidants in plasma and sputum samples: These measures will be provided by the Biochemistry Core of the UNC Clinical Nutrition Research Unit and may include reduced and oxidized glutathione, catalase, glutathione peroxidase, glutathione reductase, and superoxide dismutase.

4. Hypertonic Saline Induced Sputum procedure:

FEV1 and forced vital capacity (FVC) are measured before ozone challenge to determine the post bronchodilator baseline FEV1, and FVC values. The FEV1 values that match a 10% and 20% fall from post bronchodilator baseline are determined. An ultrasonic nebulizer is filled with 15cc of 3% hypertonic saline (inhalation grade for respiratory use only, 3% NaCl) to begin the test. The nebulizer is set to the maximum output setting and turned on. The subject is instructed to latch his/her mouth onto the nebulizer mouthpiece and breath normally (i.e., tidal breaths) for 7 minutes. The saline is nebulized through the mouthpiece in a jet stream and inhaled. The nose is not occluded for this procedure. The subject is encouraged to come off the mouthpiece at any time to cough if a sputum sample from the lower airways (i.e. not from the back of the throat) is ready for expectoration. Prior to expectoration, subjects are asked to blow their nose, rinse their mouth with water, and clear their throat to avoid the inclusion of non-airway fluid samples. The sample is expectorated into a sterile specimen jar and capped. Following the measurement of FEV1 after the first 7 minute inhalation period,

the concentration of saline is increased from 3% to 4%, provided the FEV1 falls by < 10% from the post-bronchodilator value. A volume of 15cc fills the nebulizer well on each occasion. If the FEV1 falls between 10-20% of the post bronchodilator value, the test proceeds but the concentration of saline remains the same. If the FEV1 falls by > 20% or if troublesome symptoms occur, the nebulization is discontinued and albuterol is available if necessary to relieve symptoms. Troublesome symptoms included cough, chest tightness, and general discomfort. The same procedure is followed for the final 7 minute inhalation period using 5% hypertonic saline provided the FEV1 safety parameters described above have been met. The nebulization is stopped after 21 minutes or earlier if a sputum sample of good quality is obtained (i.e. visible sputum plugs).

5. Spirometry:

Standard methodology conforming to the American Thoracic Society guidelines for measurement of spirometry will be used.

6. Fraction of Exhaled Nitric Oxide

Airway inflammation will be evaluated using the NIOX MINO device, following ATS, 2005 recommendations and the manufacturer's instructions. Since spirometry can potentially impact the nitric oxide (NO) measurement, the FeNO test needs be completed prior to spirometry. In addition, subjects should not eat or drink 1 hour prior to having the FeNO, as this may affect the results.

7. Nasal Epithelial Lining Fluid (ELF): Nasal ELF will be sampled with a small strip of Leukosorb paper inserted gently by means of direct vision into the nasal cavity laterally against the anterior portion of the inferior turbinate. Sterile saline solution is transferred into a mist bottle (the same one used for NL) and subjects are asked to moisten their nasal passages with a single spay into each nostril. A nasal clip will be applied, and the Leukosorb paper will be left for absorption for 2 minutes. Subjects will be required to breathe though the mouth during this time. Thereafter, the Leukosorb strip will be removed and immediately stored at 80°C.

8. Nasal Epithelial Cells (NEC): a non-invasive biopsy procedure will be performed to retrieve a small cluster of cells from each of the nasal cavities. For the nasal biopsy procedure, the subject will be seated comfortably in a straight-backed chair or reclining on an examination table with the head tilted as far back as possible while remaining comfortable. Subjects will be given no medication, sedation, or anesthesia for this procedure. A short, sterile plastic sampling device called a curette will be inserted into one of the nasal cavities and the surface of the nasal cavity will be stroked several times for approximately 5 seconds in order to obtain a small cluster of cells. This maneuver will be repeated on the contralateral nasal cavity using a fresh curette. The nasal biopsy may only be obtained from 1 nostril during a visit.

9. Regional Deposition and Mucociliary Clearance (MCC) procedures:

Prior to the each MCC study a transmission Co57 scan will be performed to define the lung boundaries, to assign regions of interest, and to normalize these regions for lung volume differences. A rectangular phantom containing the radioisotope Co57 (< 25 mCi) will be placed in front (5cm) of the subject sitting with his/her back to the gamma camera for 30 seconds. The transmission scan has been used by us and others to provide a delineation of lung boundaries for assessing regional deposition/clearance of the inhaled radioaerosol. Prior to the transmission scan on each study day we will place 2 spot markers of Americium241 (0.9

microcurie (uCi) each, gamma 66 KeV) on the upper and lower back of each subject during scanning (both Tc99m-SC deposition/retention and Co57 transmission). With dual isotope imaging, these spot markers will allow alignment of images for more accurate determination of regional deposition/retention. These very low radiation sources have been obtained from commercially available home smoke alarms. The placement of these markers will be determined to be outside the lung field during the transmission scan. Their location will be marked in semi-permanent ink for later placement during Tc99m deposition/retention scans. The shielded side of this source will be placed/taped onto the subject's skin.

Radiolabeled Tc99m-sulfur colloid will be delivered using a modified Pari-LL nebulizer (MMAD 9.5 um). This is a closed delivery system that produces 80 ml/sec air flow, and therefore limits the inspiratory flow rate to this value. While seated in front of a gamma camera subjects will perform single inhalations lasting ~10 seconds each from the delivery system, and will exhale at 500 ml/sec (using feedback from a flow meter in the breathing circuit). Approximately 5-10 of these inhalation maneuvers will be required to deposit an adequate radioisotope dose to the lung. Subjects will be allowed to breathe normally (off the nebulizer) in between each inspiratory maneuver. Each volunteer will practice these maneuvers prior to the actual radioaerosol inhalation to guarantee his/her proficiency. The activity of Tc99m-SC loaded in the nebulizer will be adjusted to provide an estimated 40 uCi deposited in the lung for each MCC scan. A single crystal detector will be placed at the subject's back during inhalation to monitor dose to the lung. Total inhalation time should be less than 5 minutes in all cases. Immediately following radioisotope inhalation, the subject will gargle and drink water to clear activity that deposited in the mouth into the stomach. The subject will then (within a minute of final inhalation maneuver) be seated in front of a large-field-of-view gamma camera to begin acquiring particle retention images. Serial, 2-minute gamma images will be captured continuously for the first 34 minutes following isotope delivery. Thereafter, 2 consecutive 2-minute images will be obtained at the start of every 10 minute period until 2 hours post isotope inhalation. The subject will also return the following day to obtain a 30 minute scan of 24 hour lung activity.

